## 5.4 Packaging of Medications and Supplies *Serenoa Repens* 320 mg capsules and matching placebo will be supplied in blister cards.

A kit will be prepared that will contain enough blister cards to allow for a 12-week supply plus 2 weeks. All blister cards and kits will be labeled in a manner to maintain the blind. The kits will be prepared as per section 5.1 for each of the two treatment assignments.

Each site will be sent an initial supply of kits. Kits will be assigned to participants at randomization. Additional kits will be sent to replace those assigned to participants and for the next visit for randomized participants. Additional kits will be available to be assigned to participants in the event of lost or damaged medication.

Participants will be instructed to take one capsule from the study drug package daily for the first 24 weeks, two capsules from the study drug package daily for the 2nd 24 weeks, and three capsules from the study drug package daily for the last 24 weeks. Participants will be instructed to return all used, partially used and unused blister cards to the study coordinator at the next visit, to allow for compliance counts. Medication returned by participants will be documented in their case report forms. Returned medication once documented may be destroyed on site according to site-specific procedures on file with the Data Coordinating Center.

Kits that expire or kits from participants who are dropped permanently from the study will be disposed of at each clinical site according to site-specific procedures on file with the Data Coordinating Center.

Unmasking of kits should not be necessary but in the event of a medical emergency the site should contact the Data Coordinating Center.

All medication kits will be shipped with an invoice, which should be checked to ensure the shipment is complete and undamaged. Any missing, or incorrect or damaged kits should be documented on the invoice and the Drug Distribution Center contacted immediately. The invoice should be signed by an authorized site representative and returned to the Drug Distribution Center (by Fax or Mail); a copy should be maintained in the site drug inventory record book. All kits assigned to participants should be signed out of the drug accountability records.

#### 5.5 Masking Procedure and Labeling

In order to preserve the double-masking of the trial, only the Data Coordinating Center and the drug distribution center will be unmasked. The Drug Distribution Center will be provided with the randomization sequence and treatment assignment directly by the Data Coordinating Center.

#### 5.6 Unmasking

Treatment assignment may be revealed only for reasons relating to the participant's safety or when critical therapeutic decisions are contingent on knowing the assigned study medication. Except in the most pressing circumstances, a decision to unmask must be submitted to the Steering Committee Chair or Clinical Review Committee Chair and permission in writing must be obtained before unmasking. Withdrawal of a participant from the study is not a sufficient reason to unmask.

If a treatment assignment is unmasked, the DCC will record the following key information at the time of unmasking: participant number and initials, medication kit number, date of unmasking, reason for unmasking, the name of the site investigator who requested unmasking, and the name of the Data Coordinating Center member who revealed the treatment assignment to the site investigator after authorization was received regarding that the blind be broken. This information will be forwarded to the Clinical Review Committee, DSMB and funding agency within 5 business days of unmasking.

#### 5.7 Restrictions on use of Concomitant Medications

#### 5.7.1 Exclusionary Medications

The purposes of defining exclusionary medications are: to protect participant safety by avoiding inappropriate and unsafe use of concomitant medications; and to maintain the integrity of the trial by restricting the use of medications or other agents that may affect the primary outcome measures.

The following medications are not permitted while participating in the trial. The absence of a particular medicine from this list does not imply it is not an exclusionary drug. All concomitant medications that a participant is taking should be checked to determine that the medications are not exclusionary. When there is a doubt, please consult the Physician's Desk Reference (PDR), a pharmacist, or the Chairman of the Clinical Review Committee.

#### 5.7.2 Medications not Permitted:

The following classes of medications may alter lower urinary tract symptoms or function, interfering with study measurements. Participants should be instructed to not take these classes of medications, and to call the study coordinator if they start any new medications (including over-the-counter medications). If they are taking a prohibited over-the-counter medication at the time of a study follow-up visit, they should be instructed to stop the medication. If they are taking

prohibited prescription medication, the prescribing clinician should be contacted to determine if stopping the medication would be unsafe (for example, spironolactone prescribed for congestive heart failure might not be safe to discontinue). In that case, a repeat visit should be scheduled after a two-week "washout" period (four weeks for medications with estrogenic or androgenic effects) to obtain the necessary measurements.

**Oral Alpha-agonists (pseudoephedrine and others)** 

**Anti-cholinergics** 

Anti-depressants with anticholinergic effects

**Anti-emetics** 

**Anti-Parkinsonian Agents** 

**Anti-spasmodics** 

**Cholinergics Agents** 

**Agents for Myasthenia Gravis** 

**Estrogen Preparations** 

**Androgens** 

**Anti-Androgens** 

**Anabolic Steroids** 

#### 5.8 Criteria for Treatment Discontinuation

Participants may discontinue assigned CAMUS therapy before the planned completion of study for the following reasons:

- Noncompliance. Participants who are non-compliant with respect to keeping appointments or completing required tests for the evaluation of treatment safety and efficacy may be discontinued from study treatment voluntarily, or at the discretion of the investigator.
- Voluntary withdrawal. Participants may decline to receive further therapy, or decline any study intervention at any time.

 Investigator discretion. The investigator has the right to discontinue any component of study treatment or procedures that the investigator believes could be harmful to the participant.

CAMUS participants must discontinue their assigned CAMUS therapies pursuant to the following events:

- Diagnosis of prostate cancer
- Diagnosis of bladder cancer
- The need for ongoing therapeutic anti-coagulation with Coumadin, Plavix or Heparin.
- Crossover to any open-label therapy for BPH (including phytotherapies for BPH)
- Crossover to any invasive therapy for BPH
- Unacceptable treatment toxicity
- Death

CAMUS participants who elect to or must stop their assigned study medications will be encouraged to continue scheduled follow-up visits regardless.

#### 5.9 Criteria for Study Discontinuation

All participants should be followed for 72 weeks from the date of randomization, and should be encouraged to undergo all protocol procedures. Participants may withdraw from the study at any time.

#### 6.0 ADVERSE EVENTS REPORTING

This study will utilize the NCI's Common Toxicity Criteria for Adverse Events (CTCAE) v3.0. A copy of the CTCAE version 3.0 can be downloaded from the CTEP home page (http://ctep.cancer.gov/reporting/ctc.html).

## 6.1 Classification of Adverse Events by Severity and Relationship to Study Drug Administration

Adverse Event – Any unfavorable and unintended sign (including an abnormal laboratory finding), symptom or disease regardless of whether it is considered related

to the study medications (attribution of unrelated, unlikely, possible, probable, or definite).

- **Life-Threatening Adverse Event** Any adverse event that places the participant, in view of the investigator, at immediate risk of death from the reaction.
- Serious Adverse Event (SAE) Any adverse event occurring that results in any of the following outcomes: death, a life-threatening adverse event, inpatient hospitalization or prolongation of existing hospitalization, a persistent or significant disability/incapacity, or a congenital anomaly/birth defect. Important medical events that do not result in death, are not life-threatening, or do not require hospitalization may be considered serious adverse experiences when, based upon appropriate medical judgment, they may jeopardize the participant and may require medical or surgical intervention to prevent one of the outcomes listed in the definition.
- Hospitalization All hospitalizations (or prolongation of existing hospitalization) for medical events equivalent to CTCAE grade 3, 4 or 5 must be reported.
- Attribution The determination of whether an adverse event is related to a study treatment. Attribution categories:
  - Definite The adverse event *is clearly related* to the study medication.
  - Probable The adverse event *is likely related* to the study medication.
  - Possible The adverse event *may be related* to the study medication.
  - Unlikely The adverse event *is doubtfully related* to the study medication.
  - Unrelated The adverse event *is clearly NOT related* to the study medication.

#### **6.2** Reporting of Adverse Events

All clinically significant adverse events regardless of severity, and whether or not ascribed to the study drug administration, will be recorded in the appropriate section of the Case Report Form. Participants withdrawn from the study due to adverse events will be followed by the investigator until the outcome is determined and, when appropriate,

additional written reports and documentation will be provided. All grade 3, 4 and 5 adverse events will be reviewed by the Clinical Review Committee.

All adverse events will be tabulated by treatment arm, severity grade and reported to the CAMUS Data Safety and Monitoring Board. Adverse events will be tabulated by severity grade and reported to the site. It will be the responsibility of the site principal investigator to disclose this information to the site's institutional review board.

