#### 2.0 OBJECTIVES

#### 2.1 Primary objective

The primary objective of CAMUS is to determine if Serenoa Repens reduces the AUA symptom score compared to placebo over 72 weeks of treatment and is well tolerated.

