#### 5.2 Retitration and Rechallenge with Study Medications

A participant may experience a symptomatic side effect or other abnormality (e.g., a laboratory abnormality) that either he or the investigator believes may be related to the study medication and require withdrawal. Investigators will consider the possibility of a study medication side effect especially in the event of a new, persistent abnormality in any blood test, particularly one that would have excluded a participant's enrollment at baseline, or in the event of new evidence of myocardial infarction or ischemia on the periodic study EKGs. In these circumstances, it may be prudent to attempt a rechallenge of study medication in order to ascertain more evidence of causality and to better assess severity of the adverse effect. Whether or not to perform a rechallenge is the decision of the site principal investigator; obviously, it would be inadvisable to rechallenge a patient who had a serious reaction with a high likelihood of being related to the study medication.

In the event that there is an interruption of therapy and the participant does not take the study medication for at least 14 days (e.g. due to compliance problems, lost medication, physician stopping drug for mild intolerance or minor adverse event), the participant may be retitrated on the medication.

In the event that the participant experiences a moderate or severe adverse event and it is the physician's medical judgment that the participant should be restarted on the study medication and the physician has contacted the Clinical Review Committee and received approval, the participant may be rechallenged.

Retitration or re-challenge should utilize the same kit of medication that the participant has been using or a new kit for that participant may be issued (contact the Drug Distribution Center to request an additional kit if necessary). The participant should be dosed in the following manner. The participant should start at the lowest dose (1 capsule daily) for at least 1 week (longer if physician/participant desires) and then add 1 capsule per day each week until the previous maximum dose (2 gelcaps/day or 3 gelcaps/day) is

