#### 8.2.4 Safety Analysis

Adverse event data will be summarized by treatment arm to capture the proportion of participants reporting at least one episode of a specific adverse event (incidence table), incidence of adverse events causing withdrawal, and incidence of serious adverse events. The total number of episodes for each event reported (frequency table), and the severity and attribution to treatment arm of each episode reported within body system (severity and attribution table), will also be displayed by treatment arm. Listings of adverse events by participants and event will also be provided. Comparisons of incidence of each adverse event between treatment and placebo will be performed using the two-group chi-square test, or Fisher's exact test when the assumptions for the chi-square test are not tenable. A two-sided statistical test with a significance level of 0.05 will be used for these analyses. In addition, 95% confidence intervals will be computed for differences in proportions of adverse events between study arms.

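### Section 6.2 records only clinically significant adverse events, a term left undefined, while Section 6.1 defines and Sections 6.2 and 8.2.4 analyse all adverse events, so incidence may be understated

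*Combined protocol and SAP*

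**What the plan says.** Section 6.1 defines an adverse event broadly: "Any unfavorable and unintended sign (including an abnormal laboratory finding), symptom or disease regardless of whether it is considered related". It sets no threshold of clinical importance.

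Section 6.2, first paragraph, governs what reaches the Case Report Form: "All clinically significant adverse events regardless of severity, and whether or not ascribed to the study drug administration, will be recorded".

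Section 6.2, second paragraph, describes the reporting: "All adverse events will be tabulated by treatment arm, severity grade and reported to the CAMUS Data Safety and Monitoring Board".

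Section 8.2.4 plans tables of incidence, frequency, severity and attribution, followed by a test: "Comparisons of incidence of each adverse event between treatment and placebo will be performed using the two-group chi-square test", with Fisher's exact test as the fallback. It adds: "A two-sided statistical test with a significance level of 0.05 will be used for these analyses".

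The primary objective in Section 2.1 asks whether the extract reduces the symptom score "compared to placebo over 72 weeks of treatment and is well tolerated". Section 1.1 links close tolerability monitoring to the higher-than-usual doses and makes tolerability part of the decision on a later long-term trial.

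**The concern.** The definition, the recording rule and the analysis refer to different sets of events. The definition and the analysis cover every adverse event. The recording step between them admits only those judged clinically significant, and an event that was never recorded can be neither tabulated nor tested.

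The events most exposed are symptomatic and minor. These matter here: Section 1.2 describes the adverse effects seen in previous trials of these extracts as mild and infrequent, and Section 5.2 gives "physician stopping drug for mild intolerance or minor adverse event" as one example of why dosing might be interrupted. With 11 clinical centers (Section 10.2) and no definition, thresholds could also differ between centers. At stake is whether the incidence figures that support a statement about tolerability mean what Section 8.2.4 says they mean.

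**Working it through.** The point is settled mainly by comparing texts. The arithmetic only shows why no size can be attached to it.

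**1. Events covered at each stage**

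| Stage | Section | Events covered |
|---|---|---|
| Definition | 6.1 | all, related or not |
| Entry on the form | 6.2, first paragraph | clinically significant only, any severity, any attribution |
| Tables for the monitoring board | 6.2, second paragraph | all, by arm and grade |
| Final tables and tests | 8.2.4 | each adverse event |

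The second row is narrower than the other three.

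**2. What the filter can remove.** Severity and clinical significance are separate judgements. The rule bars exclusion because an event is mild. It does not bar exclusion of an event, mild or not, that someone considers unimportant.

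**3. Whether another route captures an omitted symptom.**
- Committee review covers grades 3 to 5 (Sections 6.2 and 10.4.3).
- Expedited reporting covers serious, life-threatening or fatal events (Section 6.3).
- The laboratory comparison works from graded measured results, but names only blood counts and serum chemistries and compares only grade 3 or above (Section 8.2.3).
- The drug administration form takes the date of last use (Section 5.2). The text does not say that it names the event.
- Medical follow-up (Section 4.3.2) covers new diagnoses and treatments, but Section 8.2.4 analyses adverse event data.

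A low-grade symptom therefore depends on the filtered form.

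**4. The plan's own safety figure.** Section 8.1 states 80% power for severe laboratory events at 2.5% v 10%, 157 per arm, one-sided 0.05. The pooled-variance sample size is 128 per arm. With the continuity correction, n' = (n/4)·[1 + √(1 + 4/(n·d))]², where d = 0.075: 32 × [1 + √(1 + 4/9.6)]² ≈ 153.5, so 154, close to 157. This figure concerns measured laboratory results and is not in dispute.

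**5. Effect on the Section 8.2.4 test (illustration).** The documents give no rate for symptomatic events and no recording fraction. Both are assumed here.

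Power = Φ[(|p₂ − p₁| − 1.96·SE₀)/SE₁], with SE₀ = √[2p̄(1 − p̄)/n] and SE₁ = √{[p₁(1 − p₁) + p₂(1 − p₂)]/n}. Take n = 350/2 = 175 per arm, two-sided 0.05, and assumed true rates of 10% v 20%.

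- All recorded, 10% v 20%: (0.10 − 1.96 × 0.0382)/0.0378 ≈ 0.67; power 75%.
- Half lost in each arm, 5% v 10%: (0.05 − 1.96 × 0.0282)/0.0280 ≈ −0.19; power 43%.
- Five points of background complaints lost from each arm, 5% v 15%: (0.10 − 1.96 × 0.0321)/0.0316 ≈ 1.17; power 88%.

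At 157 per arm the three values are 70%, 39% and 84%. Recorded incidence falls in both loss patterns. Power falls in one and rises in the other.

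**The case against.** The strongest reply is that no real restriction was intended. Recording is irrespective of severity. Adverse events are assessed at all nine follow-up visits (Section 4.3.12), and the schedule in Appendix I marks the adverse event form at each. The second paragraph of Section 6.2 speaks of all adverse events. Because Section 6.1 counts any abnormal laboratory finding as an adverse event, the adjective may have been meant only to screen out trivial laboratory deviations. The Manual of Operations, which Section 8.3.1 says covers procedures and form submission, may define the term.

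That is a plausible account of intent, but it does not remove the mismatch. Assessing an event does not put it on the form if the recording rule excludes it. The Manual was not supplied, and the protocol should be consistent by itself.

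The reply does defeat several stronger readings that a reader might infer:

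- *Mild intolerance is excluded.* The text does not say so. It is lost only if judged not clinically significant.
- *Events that stop study drug will be missed.* Such an event is the least likely to be called insignificant. The mention in Section 5.2 is one example of a cause of interruption, not a forecast.
- *Each site decides.* This is a reasonable inference, since sites complete the form, but no judge is named.
- *The comparison loses power and leans toward a finding of good tolerability.* This needs proportional loss in both arms, which the documents do not establish. The other pattern in the illustration raises power.

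**Conclusion.** The concern holds as an inconsistency in the current text with one supported consequence: a symptom judged not clinically significant can go unrecorded, so the reported incidence of an event may be understated. It matters because tolerability is part of the primary objective.

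Its size is unknown. The illustration rests wholly on assumed rates and assumed patterns of loss, and its range of 43% to 88% shows that even the direction of the effect on power cannot be read from the documents. Under the double blind, omissions should be similar in the two arms, and no between-arm bias is shown. Serious events are reported separately, and events causing withdrawal are unlikely to be missed. The efficacy sample size and the stated laboratory safety power are unaffected. The change is worth making because it is cheap and removes the doubt, not because a distorted comparison has been demonstrated.

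**What to change.** In Section 6.2, delete the clinical-significance condition for signs, symptoms and diagnoses. Every event that meets the Section 6.1 definition and is reported or found at the scheduled assessments is then recorded with its CTCAE grade. State also that any event that interrupts or reduces study drug is recorded. This concerns data capture only and changes no dosing rule.

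If a filter is kept for isolated laboratory values, define it, and state that all scheduled laboratory results are summarised by arm from the measured values. Prothrombin time and urinalysis need explicit mention: they are collected (Sections 4.3.3 and 4.3.5), but the laboratory comparison in Section 8.2.3 does not name them, and it does not compare grades below 3.

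The cost is a wording change plus somewhat more low-grade events to enter and code. The assessments themselves are already scheduled.

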#### **6.3** Expedited Adverse Event Reporting

All serious adverse events or unexpected adverse events that are life threatening or fatal regardless of attribution, including death within 30 days of the last dose of study treatment, should be reported to the DCC within 24 hours or by the next business day.

#### 7.0 BPH OUTCOME EVENTS

The following BPH outcome events will be tracked on CAMUS subjects. Although not part of the primary outcome, their occurrence should prompt reconsideration of the advisability of continuing coded study medication.

- Acute urinary retention.
- Recurrent symptomatic urinary tract infections or urosepsis.
- New incontinence or progression of minor incontinence (confirmed on two successive visits).
- Initiation of active, unblinded therapy for BPH, including phytotherapy, alphablockers, 5-alpha reductase inhibitors, or any invasive therapy for BPH.

If participants initiate active unblinded therapy for BPH, they must be withdrawn from coded study medication, but should continue scheduled follow-up. If a study participant reports one of the BPH outcome events (either at a regular visit or in between visits) such as an episode of acute retention, a urinary tract infection, or initiation of open-label treatment for BPH, the study coordinator would review his medical records to confirm whether the reported event meets the definition for an outcome event.

Definitions of acute urinary retention, new incontinence or progression of minor incontinence, and recurrent symptomatic urinary tract infections are as follows:

- Acute urinary retention is the inability to urinate requiring catheterization. If the participant has an obvious cause of acute retention other than BPH (such as alpha sympathomimetic medications or anesthesia), he should have a trial period of catheter removal. If he is still unable to void, he meets the definition of acute urinary retention.
- *New incontinence* is a new requirement for daily use of a pad or device for incontinence. *Progression of minor incontinence* is an increase of six or more points from SV2.0 on the ICS*male*IS.
- Recurrent symptomatic urinary tract infection is two or more symptomatic urinary tract infections documented by positive culture, separated by curative antibiotic therapy, within one year. Curative therapy must be documented by a negative interim culture obtained at least one week after completion of the course of antibiotics. Urosepsis is a severe urinary tract infection with the same bacterial pathogen isolated from both the participant's blood and urine.
- Initiation of active, unblinded therapy for BPH is defined as the participant knowingly taking a phytotherapy, alpha-blocker, or a 5-alpha reductase inhibitor specifically for BPH for more than 30 days; or undergoing an invasive therapy specifically for BPH. Examples of medications for BPH are provided in Section 5.5. Invasive procedures for BPH include open and transurethral prostatectomy, transurethral electrovaporization, transurethral incision, laser therapy (coagulation, vaporization, or holmium resection), transurethral microwave heat therapy, and transurethral needle ablation (TUNA). If participants begin a BPH medication unknowingly or for another purpose (for example, an alpha-blocker prescribed for hypertension), they can be withdrawn from the medications usually in consultation with the prescribing clinician without being considered to have reached a BPH outcome event. They should be "washed out" before additional study measurements are taken (see Section 5.5). Similarly, participants who take a brief course (up to 30)

days) of a BPH medication before they stop should not be considered to have reached a BPH outcome event.

